6. Study procedures: participants will be randomized in a 1:1 ratio to receive ceftriaxone plus doxycycline or BPG plus doxycycline. Randomization will be stratified by the stage of syphilis and RPR titer at baseline.

Arm 1: single-dose ceftriaxone (1g intramuscularly once) plus doxycycline (100 mg orally twice daily for 7 days)

Arm 2: single-dose BPG (2.4 MU intramuscularly once) plus doxycycline (100 mg orally twice daily for 7 days)

7. Baseline and follow-up testing:

Proof of concept phase: (enrolled 50 participants in each group)

- (1) Questionnaire for socio-epidemiologic characteristics and sexual history at baseline and weeks 24, 48
- (2) Serum RPR at baseline and weeks 4, 12, 24, 36, and 48
- (3) *T. pallidum* PCR (TP-PCR) for self-collected specimens from oral rinse, urethral, and rectal sites at baseline, weeks 1, 2, 3, 4, 12, 24, 36, and 48 (specimens collected in weeks 1, 2, and 3 were optional)
- (4) Bacterial STIs (*C. trachomatis*, *N. gonorrhoeae*, *Mycoplasma genitalium*, *M. hominis*, *Ureaplasma urealyticum*, *U. parvum*) for self-collected specimens from oral rinse, urethral, and rectal sites at baseline and week 4
- (5) Resistance-associated mutations (RAM) of *T. pallidum* and other sexually transmitted bacteria at baseline

	Baseline	Wk1 (±2 days)	Wk2 (±2 days)	Wk3 (±2 days)	Wk4 (±2 days)	Wk12 (±2 weeks)	Wk24 (±2 weeks)	Wk36 (±2 weeks)	Wk48 (±2 weeks)
Questionnaire	v						v		v
Doxycycline compliance record		v							
RPR	v				v	v	v	v	v
TP-PCR	v	v	v	v	v	v	v	v	v
		(optional)							
Bacterial STIs	v				v				
RAM	v								

Continuation phase: (enrolled 100 participants in each group)

- (1) Questionnaire for socio-epidemiologic characteristics and sexual history at baseline and

weeks 24, 48

(2) Serum RPR at baseline and weeks 4, 12, 24, 36, and 48

(3) *T. pallidum* PCR (TP-PCR) for self-collected specimens from oral rinse, urethral, and rectal sites at baseline, weeks 4, 12, 24, 36, and 48

(4) Bacterial STIs (*C. trachomatis*, *N. gonorrhoeae*, *M. genitalium*, *M. hominis*, *U. urealyticum*, *U. parvum*) for self-collected specimens from oral rinse, urethral, and rectal sites at baseline and week 4

(5) Resistance-associated mutations (RAM) of *T. pallidum* and other sexually transmitted bacteria at baseline

	Baseline	Wk1 (±2 days)	Wk2 (±2 days)	Wk3 (±2 days)	Wk4 (±2 days)	Wk12 (±2 weeks)	Wk24 (±2 weeks)	Wk36 (±2 weeks)	Wk48 (±2 weeks)
Questionnaire	v						v		v
Doxycycline compliance record		v							
RPR	v				v	v	v	v	v

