TP-PCR	v				v	v	v	v	v
Bacterial STIs	v				v				
RAM	v								

8. Duration of study: Participants will be followed for at least 48 weeks.

9. Primary outcome:

Serologic response at month 6 (defined as either a 4-fold or greater decline in RPR titer compared to baseline or being RPR-nonreactive)

10. Secondary outcomes:

(1) Microbiologic response of syphilis (defined as *T. pallidum* PCR Ct value >38) at week 4

(2) Microbiologic response of bacterial STIs (defined as negative PCR results) at week 4

(3) Serologic response at months 3 and 12

(4) Safety of study treatment recorded by using a diary (all adverse events will be coded and graded according to Common Terminology Criteria for Adverse Events [CTCAE] v4.0.)

(5) Adherence evaluation (the noting of tablet intake in the diary for the 7 days of the treatment period)

11. Futility stopping rules:

(1) In the proof-of-concept phase, microbiologic and/or serologic response of syphilis

(microbiologic response was defined as *T. pallidum* PCR Ct value >38, and serologic response was defined as at least a 4-fold decrease in RPR titers) at week 4 will be compared between study groups. The non-inferiority margin of 10% will be used as the futility stopping rule in the proof-of-concept phase.

(2) Participants with treatment failure at week 24 will receive standard-of-care treatment (BPG 2.4 MU intramuscularly once). Treatment failure is defined as at least a 4-fold increase in RPR titers compared with the baseline RPR or at least a 4-fold increase in RPR titers after achieving serologic response during follow-up. Participants who received additional treatment with an antimicrobial active against *T. pallidum* (i.e. penicillins, third-generation cepheems, doxycycline, or macrolides) will also be excluded from the study.

(3) The continuation phase will be conducted only if microbiologic response of syphilis is non-inferior in the ceftriaxone plus doxycycline group compared with the BPG plus doxycycline group.

Laboratory investigations

1. *T. pallidum* PCR:

T. pallidum PCR will be performed on specimens from oral rinse, urine, rectal sites, blood, and lesions of syphilis. Treponemal DNA will be extracted with the QIAamp DNA mini Kit. The diagnostic PCR assay will be used to amplify the 47 kDa protein membrane gene (*tpp47*).

2. Bacterial STIs screening:

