The screening for bacterial STIs, including *C. trachomatis*, *N. gonorrhoeae*, *Trichomonas vaginalis*, *Mycoplasma* spp., and *Ureaplasma* spp.) will be performed on self-collected specimens from oral rinse, urethral, and rectal sites with the use of multiplex real-time PCR assay on an automated system.

3. Resistance-associated mutation of *T. pallidum*

Single-nucleotide polymorphisms (SNPs) will be determined at positions A2058G or A2059G of the 23S rRNA gene, as well as positions 965–967, 926–928, 939 and 1058 of the 16S rRNA gene.

Statistical analysis

According to the previous randomized controlled, open-label study conducted by Cao Y et al, the serological response of early syphilis at 6 months of follow up was observed in 90.2% in ceftriaxone group and 78.0% in BPG group.¹⁰ Therefore, at least 150 participants would be

required for each treatment group to detect a between-group difference, with a two-sided significance level of 5% and a power of 80%. The intention-to-treat population is defined as all patients who undergo randomization except for those who do not provide consent for the use of their data. The analyses will be performed through the FDA snapshot algorithm in the ITT population, which categorizes outcomes into success, failure, and no data in window. The Categorical variables will be compared by Fisher's exact test or Chi-square test. Non-categorical variables will be compared by Mann-Whitney U test. Factors with P value ≤ 0.2 , or with biological significance will be included for multivariate analysis. Logistic regression analysis will be used to determine the factors associated with serologic responses after treatment. All comparisons will be two-tailed and a P value <0.05 is considered significant. All statistical analyses were performed with the use of STATA software version 17.0 (Stata Corporation, College Station, TX).

References

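### Every comparison with P<0.05 is called significant, with no hierarchy, correction or exploratory label for the secondary outcomes and the factor analysis

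*Combined protocol and SAP*

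**What the plan says.** Item 9 of the Methods names a single primary outcome, serologic response at month 6. Item 10 lists five secondary items. Three concern efficacy and give four endpoints:

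- T. pallidum PCR response at week 4;
- "Microbiologic response of bacterial STIs (defined as negative PCR results) at week 4";
- "Serologic response at months 3 and 12", which is two time points.

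The other two are safety and adherence.

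The Statistical analysis section sizes the trial on the month-6 response, with the number "required for each treatment group to detect a between-group difference, with a two-sided significance level of 5% and a power of 80"%. For factors it says: "Logistic regression analysis will be used to determine the factors associated with serologic responses after treatment". Candidates enter the multivariable model if P≤0.2 or if judged biologically important; they are not listed. The section then gives the general rule: "All comparisons will be two-tailed and a P value <0.05 is considered significant".

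The document contains no testing order, alpha split, adjustment or family-wise target, and it labels no analysis exploratory or descriptive.

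**The concern.** The plan is not merely silent on multiplicity. It says outright that any P value under 0.05 counts as significant, whichever outcome or factor produced it.

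The secondaries affected could carry claims. Months 3 and 12 read the primary variable at other times, so if month 6 shows no difference, a chance result at either would still be declared significant. The Background motivates the regimen partly by sexually transmitted co-infections, and only the bacterial STI secondary addresses those. The unit of that outcome (composite, organism or anatomical site) is not fixed; item 7 lists six organisms and three sites. A baseline factor that survives the screen can also be declared significant under the same rule.

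What is at stake is how far a reader can trust the word significant when it is attached to anything other than the month-6 comparison.

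**Working it through.** **The plan's own figures.** The plan states no family-wise error rate, so there is none to reproduce. Its only error rate is 5% two-sided per test. Its sample size of 150 per arm does not enter the error-rate formulas below, but for completeness, with 90.2% against 78.0%:

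n = [1.96·√(2·0.841·0.159) + 0.842·√(0.902·0.098 + 0.78·0.22)]² / 0.122² ≈ 140 per arm

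With continuity correction it is 156, and power at 150 is 82.7%. That is a separate matter.

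**Inputs**
- Level per test: 0.05 two-sided (Statistical analysis).
- Efficacy secondaries: k = 4 (item 10).
- Correlation ρ between test statistics: not given, so assumed at 0, 0.5 and 0.8.
- Number of candidate factors: not given, so assumed at 10 to 20.

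**Which nulls can be true?** The Background says that BPG does not treat N. gonorrhoeae and that ceftriaxone does. A real between-arm difference is therefore plausible for the bacterial STI outcome, and a real difference cannot produce a false positive. I therefore take k = 3 (that outcome removed) as well as k = 4.

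**Formula.** With all k nulls true:
- Independent tests: 1 − 0.95^k.
- Equicorrelated normal statistics: 1 − ∫ φ(u)·[Φ((1.96 − √ρ·u)/√(1−ρ)) − Φ((−1.96 − √ρ·u)/√(1−ρ))]^k du, integrated numerically.

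| True nulls | ρ = 0 | ρ = 0.5 | ρ = 0.8 |
|---|---|---|---|
| 3 | 14.3% | 12.5% | 9.8% |
| 4 | 18.5% | 15.6% | 11.4% |

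For example, 1 − 0.95³ = 0.143 and 1 − 0.95⁴ = 0.185.

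**If organisms are tested singly.** Six organism tests replace the one composite, so k = 3 + 6 = 9. Independence gives 1 − 0.95⁹ = 37.0%. If N. gonorrhoeae is a true difference, k = 8 and 1 − 0.95⁸ = 33.7%. The same integral at ρ = 0.8 gives 16.6% and 15.8%.

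**Fisher's exact test.** The plan allows either Fisher's test or chi-square. At 150 per arm, Fisher's actual size is about 3.3% when both arms respond at 90% and 3.6% at 78%. Four independent tests then give 1 − 0.967⁴ = 12.6% to 1 − 0.964⁴ = 13.6%, against 18.5% at the nominal level. Three give about 10%.

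**Factor analysis, a separate family.** For independent null factors, 1 − 0.95¹⁰ = 40% and 1 − 0.95²⁰ = 64%. The P≤0.2 screen gives little protection, because a factor that falls below 0.05 by chance on its own has already passed it.

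**The case against.** The strongest case on the other side is that nothing confirmatory is damaged. There is one primary outcome, the secondaries sit under their own heading, and the 5% level of the month-6 test is unaffected by what is tested beside it. The plan never undertakes to hold 5% across the secondaries. All of that stands. A reader might infer that the trial's stated 5% is broken, or that secondaries are formally given the primary's status; the documents support neither.

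A reader might also want a larger headline, such as 16–30% for all secondaries and factors together. The documents do not support that as one number:

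- It depends on a test count and a correlation that the plan does not give.
- Its upper part needs organism-by-organism tests, whereas item 10 lists one bacterial STI response, or formal between-arm tests of safety and adherence, which the plan does not announce.
- It leaves out the factor analysis, whose size is unknown.
- It assumes no true difference anywhere, which the Background contradicts for N. gonorrhoeae.

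Nor should a chlamydia benefit be read as a between-arm claim, since both arms receive the same doxycycline course (item 6).

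Item 11 uses week-4 response with a 10% margin to decide whether the continuation phase proceeds. That is a go/no-go rule; it neither orders nor protects the final secondary tests.

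It can also be said that a screened regression is exploratory in practice. Probably so, but the written rule still lets its results be called significant.

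**Conclusion.** The concern holds in limited form. Followed as written, the plan allows chance findings among the efficacy secondaries and screened factors to be declared significant.

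For the efficacy secondaries, the chance of at least one such finding is about 10–19%. This assumes three to four true nulls, equicorrelated statistics with correlation from 0.8 to 0, and tests at their nominal 5%. Fisher's test would bring it down somewhat; separate organism tests would raise it. For factors, 40–64% rests on an assumed 10–20 independent null candidates and should be reported apart. The primary comparison is untouched. This is a cheap improvement to what the trial can claim, not a flaw in its main result.

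**What to change.** Replace the general significance sentence with:

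> Serologic response at month 6 is the only confirmatory comparison. All secondary outcomes, organism-level results and the logistic regression of factors are exploratory, reported as estimates with 95% confidence intervals without multiplicity adjustment, and are not declared statistically significant.

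The sample-size paragraph still states the two-sided 5% level. The change needs no extra participants, visits or assays, and should be made before the data are analysed.

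The cost is real: no secondary result could be called significant at any P value, and that includes the co-infection result. If the sponsor wants a confirmatory claim on named secondaries, it may prespecify the Holm procedure across them; with four, the smallest P value would be compared with 0.05/4 = 0.0125.

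Any gating on the primary should wait until the objective is settled. Item 1 of the Methods calls the trial non-inferiority, whereas the Statistical analysis section sizes it to detect a difference. If the gate were a two-sided 5% test of difference and the regimens were truly equal, it would stay closed about 95% of the time and bar every secondary claim. Those two passages must be reconciled first.

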early syphilis; in addition, ceftriaxone (500 mg intramuscularly once) is effective for treating *N. gonorrhoeae* infection, and doxycycline (100 mg orally twice daily for 7 days) effective for treating *C. trachomatis* infection.⁸ However, the current suggested dose of ceftriaxone for early syphilis (1 g intramuscularly or intravenously once daily for 10-14 days) is inconvenient as an outpatient treatment option. Ceftriaxone is long-acting, with treponemacidal levels remaining at 24 hours following injection. According to a small clinical trial, single-dose ceftriaxone achieved a serological response similar to that of BPG.⁹ Considering the high rate of sexually transmitted co-infections, combination therapy of single-dose ceftriaxone plus 7-day doxycycline for early syphilis may provide convenience and benefit to treatment of *N. gonorrhoeae* and *C. trachomatis* co-infections at a single clinic encounter. In the present study, we aim to compare the efficacy of ceftriaxone plus doxycycline versus BPG plus doxycycline as the treatment for early syphilis among PLWH.

Methods

1. Study design: randomized controlled, open-label, non-inferiority study

2. Study site: infectious diseases clinics at the National Taiwan University Hospital (NTUH)

3. Study duration: 2022-2025

4. Enrolled criteria:

(1) PLWH aged 20 years or more

(2) PLWH with early syphilis (i.e. primary, secondary, or early latent syphilis), confirmed by a positive rapid plasma reagin (RPR) titer with a reactive *Treponema pallidum* particle agglutination (TPPA) assay.

(3) PLWH has provided informed consent

*A participant with repeated syphilis can be repeated enrolled after signing an informed consent if the previous episode of early syphilis was successfully treated with achieving at least a 4-fold decrease in RPR titers and 48-week follow-up is completed.

5. Exclusion criteria:

(1) PLWH with RPR titers of less than 4

(2) Exposure to antibiotics with activity against *T. pallidum*, such as penicillins, third-generation cepheems, doxycycline, or macrolides, within the preceding 4 weeks

(3) A known or suspected infection other than syphilis requiring additional treatment with an antimicrobial active against *T. pallidum*

(4) A history of intolerance to penicillin, ceftriaxone, or doxycycline

(5) Pregnancy

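### The trial is labelled non-inferiority, but for the month-6 primary outcome the plan gives only a two-sided difference test and no margin, so it has no valid basis for concluding non-inferiority unless ceftriaxone plus doxycycline is significantly better

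*Combined protocol and SAP*

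**What the plan says.** Methods item 1 gives the design as "Study design: randomized controlled, open-label, non-inferiority study". The Background states the aim without a hypothesis or margin: "we aim to compare the efficacy of ceftriaxone plus doxycycline versus BPG plus doxycycline". Allocation is equal (Methods item 6), and the primary outcome in item 9 is binary: "Serologic response at month 6 (defined as either a 4-fold or greater decline in RPR titer compared to baseline or being RPR-nonreactive".

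Non-inferiority appears in two other places, both in item 11 and both tied to the proof-of-concept phase. Item 11(1) says "The non-inferiority margin of 10% will be used as the futility stopping rule in the proof-of-concept phase", for week-4 response. Item 11(3) says "The continuation phase will be conducted only if microbiologic response of syphilis is non-inferior" in the ceftriaxone arm. Neither gives a confidence level or an interval.

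The Statistical analysis section cites 6-month response of 90.2% with ceftriaxone and 78.0% with BPG. From these it asks for at least 150 per group to show a difference, at two-sided 5% and 80% power. It assigns categorical variables to Fisher's exact or chi-square tests and ends with the general rule "All comparisons will be two-tailed and a P value <0.05 is considered significant". Logistic regression is reserved for factors associated with response. The section contains no margin, no non-inferiority hypothesis and no confidence interval for a difference.

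**The concern.** A non-inferiority trial needs a margin for its primary outcome and a rule that compares the plausible size of any deficit with that margin. Here the month-6 outcome has neither. It inherits a test of whether the two rates differ, which is a different question. When the regimens are similar, which is when a non-inferiority design matters, that test will nearly always return a non-significant P value. Such a P value does not show that a meaningful deficit has been excluded.

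The risk is that the main conclusion rests either on a non-significant result or on a margin and interval chosen after the data are known. In an open-label trial the second would be hard to defend.

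**Working it through.** **Inputs from the documents.** 150 per arm, 1:1; cited rates 90.2% and 78.0%; two-sided 5%; 80% power; Fisher or chi-square; 10-point margin (week 4 only). **Assumptions.** The 10-point margin is carried to month 6; true rates are varied as shown; every participant has an outcome.

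**1. What the stated sample size is for.** Pooled-variance formula for a difference, with mean rate (0.902 + 0.780)/2 = 0.841:

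n = [1.96·√(2·0.841·0.159) + 0.8416·√(0.902·0.098 + 0.780·0.220)]² / 0.122² = 139.8, so 140 per arm.

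With continuity correction it is 156. The stated 150 lies between them, so it is a plausible rounding of a difference calculation, with no non-inferiority margin in it. Power for the difference at 150 is about 83% by the same approximation.

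**2. How often the planned test is non-significant.** Exact enumeration of two independent binomials, n = 150 each, summing the probability of all outcomes with two-sided P ≥ 0.05 (chi-square without continuity correction):

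| True ceftriaxone vs BPG | Chi-square | Fisher |
|---|---|---|
| Equal (78%, 84.1% or 90.2%) | about 95% | 96-97% |
| 68% vs 78% | 50.1% | 55.0% |
| 80% vs 90% | 31.4% | 37.1% |

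For comparison, a Newcombe 95% interval with its lower limit required to exceed -10 points would declare non-inferiority in 2.6% of trials at 68% vs 78% and 2.5% at 80% vs 90%.

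**3. One concrete result.** Suppose 108/150 (72%) respond on ceftriaxone and 117/150 (78%) on BPG.
- Chi-square: pooled rate 225/300 = 0.75; standard error √(0.75·0.25·2/150) = 0.05; z = -0.06/0.05 = -1.2; P = 0.23. Fisher gives P = 0.29.
- Newcombe lower limit: the Wilson lower limit for 72% is 64.3%, and the Wilson upper limit for 78% is 83.9%. The limit is -6.0 - √[(72.0 - 64.3)² + (83.9 - 78.0)²] = -15.7 points.

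The planned test finds no significant difference, while the data remain compatible with a deficit well beyond 10 points. Even an observed 10-point deficit (102/150 vs 117/150) gives P = 0.051 by chi-square and 0.068 by Fisher.

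**4. What 150 per arm gives under a non-inferiority rule.** With equal true rate p, a 10-point margin, one-sided 2.5% and 80% power, n = (1.96 + 0.8416)²·2p(1-p)/0.10². Power at 150 is from exact enumeration with the Newcombe interval.

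| Equal true rate | n per arm for 80% power | Power at 150 |
|---|---|---|
| 78% | 270 | 56% |
| 84.1% (midpoint of cited rates) | 210 | 65% |
| 90.2% | 139 | 81% |

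If the cited 90.2% vs 78.0% is the truth, power at 150 exceeds 99%.

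**The case against.** The best defence is that the plan can sometimes deliver. A significant result favouring ceftriaxone plus doxycycline implies non-inferiority, and that is the scenario the trial is sized for. Under 90.2% vs 78.0% it occurs in 79% (Fisher) to 83% (chi-square) of trials. This stands. A reader might infer that the planned analysis can never support non-inferiority; that goes too far.

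A reader might also take the 50-55% as the plan's rate of wrongly accepting an inferior regimen. The documents do not support that either. These are rates of non-significance, and they become false acceptances only if someone reads P ≥ 0.05 as non-inferiority. The plan nowhere says it will.

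Third, the Statistical analysis section names no test for the primary outcome; Fisher or chi-square reaches it by implication. This means the defect is better described as a missing primary non-inferiority analysis than as a wrong test expressly chosen. It does not supply the missing analysis.

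Finally, one might say that the plan already has a 10% margin. Item 11(1) confines it to the proof-of-concept phase at week 4, and no sentence extends it to month 6.

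**Conclusion.** The point holds in a limited form. The declared objective and the only decision rule reaching the primary outcome do not match. Outside a significant win for ceftriaxone plus doxycycline, the plan has no valid route to a non-inferiority conclusion. With equal true rates that leaves about 95-97% of trials with a non-significant result and no criterion for interpreting it. With a true 10-point deficit, 31% to 55% of trials are non-significant, depending on the rates and on which permitted test is used, so reading non-significance as non-inferiority would often be wrong.

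The mismatch itself is read directly from the text. The percentages rest on 150 per arm with complete outcomes, and the power figures also rest on a 10-point month-6 margin that the sponsor has not stated. This should be corrected before the analysis, because it determines whether the trial can answer its own question.

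**What to change.** Before analysis, replace the primary test with wording along these lines: the primary analysis is the difference in month-6 serologic response, ceftriaxone plus doxycycline minus BPG plus doxycycline, in the snapshot intention-to-treat population, with a two-sided 95% confidence interval (for example Newcombe or Miettinen-Nurminen). Non-inferiority is concluded only if the lower limit lies above minus the pre-specified margin. Superiority is tested only after non-inferiority is met.

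Two items need the sponsor's decision:
- **Margin.** The 10 points of item 11(1) is the natural candidate, but it must be confirmed and justified for month 6.
- **Missing data.** State how snapshot participants with no result in the visit window are counted in the difference.

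Keep Fisher and chi-square for descriptive comparisons.

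The text change is about a paragraph and needs no new data, but it would be wrong to call it free. Restate the 80% power as applying to the difference test under the cited rates. Beside it give the non-inferiority power at 150 per arm (56%, 65% and 81% at equal rates of 78%, 84.1% and 90.2% with a 10-point margin), and either justify the sample size on that basis or accept and disclose the shortfall.
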